## DOCUMENT HISTORY

Version	Date	Author(s)	Brief Summary of Changes
1.0	02 Oct 2014	[name]	Original
2.0	24 Nov 2015	[name]	Clarified the timing of the 2 nd interim analysis of overall survival; added biomarkers to baseline characteristics; other changes. Refer to Section 8.2 for Details.
3.0	13 Apr 2016	[name]	In Section 3.5.2, the estimated numbers of OS events at each of OS interim analyses and final analysis are provided.  Lymph node response rate and hematological improvement rate are removed from the hierarchy of inferential testing in secondary endpoints.
4.0	9 May 2017	[name]	Update to Verstem as Sponsor, updates due to protocol amendment 3 including removal of 3 year limit on treatment duration.

## LIST OF ABBREVIATIONS

Abbreviation	Description
ADaM	Analysis Data Model
AE	Adverse Event
ANCOVA	Analysis of Covariance
AT	All-Treated
ALT	Alanine Aminotransferase
ANC	Absolute Neutrophil Count
AST	Aspartate Aminotransferase
ATC	Anatomical Therapeutic Chemical
BID	Twice a day
BOR	Best Overall Response
BUN	Blood Urea Nitrogen
CI	Confidence Interval
CLL	Chronic Lymphocytic Leukemia
CMH	Cochran–Mantel–Haenszel
CO2	Bicarbonate
CR	Complete Response
CRi	Complete Response with Incomplete Marrow Recovery
CS	Abnormal and Clinically Significant
CTCAE	Common Terminology Criteria for Adverse Events
DOR	Duration of Response
ECG	Electrocardiogram
ECOG	Eastern Cooperative Oncology Group
eCRF	Electronic Case Report Form
eDISH	Evaluation of Drug Induced Serious Hepatotoxicity
EQ-5D	European Quality of Life-5 Dimensions
FACIT-F	Functional Assessment of Chronic Illness Therapy-Fatigue
FACT-G	The Functional Assessment of Cancer Therapy - General

Abbreviation	Description
HR	Hazard Ratio
IDMC	Independent Data Monitoring Committee
IPI-145	(S)-3-(1-(9H-purin-6-ylamino)ethyl)-8-chloro-2-phenylisoquinolin-1(2H)-one
IPCW	Inverse Probability of Censoring Weighted
IRC	Independent Review Committee
IRT	Interactive Response Technology
ITT	Intent-To-Treat
IV	Intravenous
IWCLL	International Workshop on Chronic Lymphocytic Leukemia
IWG	International Working Group
LC/MS/MS	Liquid Chromatography-tandem Mass Spectrometry
LDH	Lactate Dehydrogenase
LFT	Liver Function Test
MedDRA	Medical Dictionary for Regulatory Activities
MEOI	Medical Events of interest
MMRM	Mixed Effect Repeated Measures
MRD	Minimal Residual Disease
NCI	National Cancer Institute
NCS	Abnormal but Not Clinically Significant
NED	No Evidence of Disease
ORR	Overall Response Rate
OS	Overall Survival
PD	Progressive Disease
PFS	Progression-Free Survival
PK	Pharmacokinetics
PP	Per-Protocol
PR	Partial Response
PRwL	PR with Lymphocytosis

---

Abbreviation	Description
PT	Preferred Term
QoL	Quality of Life
RBC	Red Blood Cell
RPSFT	Rank Preserving Structural Failure Time
SAE	Serious Adverse Event
SAP	Statistical Analysis Plan
SD	Stable Disease
SI	Standard International System of Units
SLL	Small Lymphocytic Lymphoma
SOC	System Organ Class
SPD	Sum of Products
TEAE	Treatment Emergent Adverse Event
TTR	Time to Response
UNK	Unknown
VAS	Visual Analog Scale
WHO	World Health Organization
WHO-DD	World Health Organization Drug Dictionary

## 1 INTRODUCTION

This is the statistical analysis plan (SAP) for study IPI-145-07, *A phase 3 study of IPI-145 versus ofatumumab in subjects with relapsed or refractory chronic lymphocytic leukemia/small lymphocytic lymphoma*. This SAP is prepared according to Amendment 3 of the protocol, dated 09 February 2017.

## 2 STUDY OBJECTIVES

### 2.1 Primary Objective

The primary objective of this trial is to examine the efficacy of duvelisib (IPI-145) monotherapy versus ofatumumab monotherapy in subjects with relapsed or refractory Chronic Lymphocytic Leukemia (CLL) or Small Lymphocytic Lymphoma (SLL).

### 2.2 Secondary Objectives

- To determine the safety of duvelisib in subjects with CLL or SLL
- To evaluate the pharmacokinetics (PK) of duvelisib and, if applicable, its metabolite(s)

### 2.3 Exploratory Objectives

- To evaluate the health-related quality of life (QoL) of subjects
- To evaluate pharmacodynamic biomarkers of duvelisib
- To evaluate biomarkers that may predict duvelisib clinical activity and/or safety
- To evaluate mechanisms of resistance in subjects who exhibit disease progression while being treated with duvelisib or ofatumumab
- To evaluate genomic features of tumors predictive of response in subjects treated with duvelisib or ofatumumab

### 3 STUDY DESIGN

#### 3.1 Overview

Study IPI-145-07 is a two-arm, randomized (1:1 ratio), open-label, phase 3, superiority trial designed to evaluate the efficacy and safety of duvelisib compared to ofatumumab.

Subjects who meet all the eligibility criteria at Screening will return to the clinic on Day 1 to receive their first dose of study drug (randomized to either duvelisib or ofatumumab). The first treatment cycle for each treatment arm will be 3 weeks (21±2 days). Subsequent treatment cycles will be 4 weeks (28±4 days).

Subjects randomized to duvelisib will be given a starting dose of 25 mg duvelisib administered orally twice daily (BID) initially in a 21-day treatment cycle followed by 28-day treatment cycles for up to 18 cycles or until disease progression or unacceptable toxicity (whichever comes first). After completing approximately 18 cycles of treatment, subjects who, in the opinion of the investigator, may derive benefit from continued treatment may receive additional cycles of duvelisib until disease progression or unacceptable toxicity. Subjects randomized to ofatumumab will receive treatment consistent with the approved product labeling: 8 weekly infusions, starting with an initial IV dose of 300 mg ofatumumab on Day 1 followed by seven weekly doses of 2000 mg. Thereafter, subjects will receive 2000 mg ofatumumab once every month for four months or until disease progression or unacceptable toxicity (whichever comes first), as outlined in the schedule of assessments. Administration of ofatumumab will not exceed the 12 doses (within 7 cycles) as described in the prescribing information.

Subjects will be followed for survival for up to 6 years (or other duration as specified by the protocol) from randomization or until death. Follow-up visits will occur every 6 months which can be conducted through a telephone interview.

#### 3.2 Sample Size Consideration

This study employs a randomized, open-label, parallel design to assess the potential superiority of duvelisib treatment over ofatumumab treatment on progression-free survival (PFS) in CLL or SLL subjects.

The sample size was determined to provide sufficient power to test the primary endpoint of PFS in a group sequential design with one planned interim analysis.

Assuming an exponential distribution for PFS, a total of 185 PFS events (deaths or progressions) will provide approximately 93% power to detect a hazard ratio of 0.6 (median PFS of 9 months in the ofatumumab group versus 15 months in the duvelisib group) using a one-sided log-rank test at a 2.5% overall significance level (ie, alpha of 0.025). The study design employs the Lan-DeMets spending function for O'Brien-Fleming boundary as the alpha spending function and the Hwang-Shih-DeCani gamma (-4) spending function as the beta spending function. A total of 300 subjects will be randomized in a 1:1 ratio to receive either ofatumumab or duvelisib. Assuming a peak accrual rate of 30 subjects per month with 11 months for accrual ramp-up and a 4% cumulative dropout rate per year, the enrollment would complete in 16 months, with the final

analysis for PFS estimated to occur approximately 27.5 months from the randomization of the first subject.

### 3.3 Randomization

Once a subject has met all entry criteria, the Interactive Response Technology (IRT) will be used to generate a distinct subject identifier. If a subject discontinues from the study, the subject identifier will not be reused and the subject will not be allowed to re-enter the study.

Eligible subjects will be randomized via IRT in a 1:1 ratio to one of two treatment arms:

- Arm 1: duvelisib 25 mg BID
- Arm 2: Ofatumumab

In order to ensure subject balance between treatment groups, study subjects will be stratified by the following:

- High risk cytogenetics (presence vs absence of del[17p])
- Refractory/early relapse to purine analog based treatment (progression <12 months after fludarabine/pentostatin: yes vs no)
- Grade 4 cytopenia(s) (presence vs absence of neutropenia or thrombocytopenia at baseline)

First dose is to occur within 7 days of randomization after all screening assessments have been completed.

### 3.4 Blinding

This study is open-label and Investigators, site staff, Sponsor and Sponsor designees will have access to treatment assignments for individual subjects. To reduce bias, a blinded independent central review of disease status will be conducted, which will be blinded to individual subject treatment assignments. Investigators, site staff, Sponsor and Sponsor designees will only have access to blinded (pooled) aggregate study data, except for a select number of Sponsor staff, who may review aggregate SAEs and Medical Events of Interest (MEOI) data by treatment groups.

### 3.5 Planned Analyses

Interim and final analyses are planned for PFS and OS. For an interim analysis, the actual p-value boundaries will be calculated based on the actual number of PFS and OS events at the analysis. For the final analysis, the actual p-value boundary for efficacy will be calculated based on the actual number of PFS and OS events at the interim analysis (or analyses) and the final analysis.

The Independent Data Monitoring Committee (IDMC) will review PFS, OS and other efficacy data at the time of PFS interim analysis. The list of IDMC deliverables, including tables and listings, is included in the IDMC charter. These deliverables will be based on the methods described in this SAP.

### 3.5.1 Planned Analyses for PFS

There will be two planned analyses for PFS, one interim analysis and one final analysis. After approximately 50% of the planned PFS events (ie, 93 PFS events) have been observed based on the blinded, independent, central review, an interim analysis of efficacy will be performed.

At the interim analysis, PFS will be tested at the alpha level based on the Lan-DeMets alpha spending function for the O'Brien-Fleming boundary with the opportunity to stop the study (other than survival follow-up) for overwhelming evidence of efficacy. If the interim analysis occurs at exactly 50% of the planned events, the criterion of stopping for efficacy is one-sided p-value of 0.0015 (corresponding approximately to a HR of 0.540). In the meantime, PFS will also be tested at the alpha level for futility based on the alpha and beta spending functions specified for the study design. If the interim analysis occurs at exactly 50% of the planned events, the criterion of stopping for futility is one-sided p-value of 0.4791 (corresponding approximately to a HR of 0.990). The futility boundary of this study is non-binding, meaning that the Type I error is properly controlled even if the study is continued after the futility boundary for PFS is crossed at the interim analysis. Under the protocol design assumptions (eg, the study is fully enrolled in 16 months), the interim analysis is expected to occur approximately 17 months after the first subject is randomized.

If the study is not stopped at the interim analysis, the final analysis will be performed when approximately 185 PFS events have occurred in the study. If the interim analysis and the final analysis occur at exactly 93 and 185 PFS events, the criterion of statistical significance (ie, boundary for efficacy) is one-sided p-value of 0.0245 (corresponding approximately to a HR of 0.748).

### 3.5.2 Planned Analyses for OS

There will be three planned analyses for OS: two interim analyses and one final analysis. The first interim analysis of OS will be performed at the time of the planned PFS interim analysis after 93 PFS events have occurred. The estimated number of OS events at this first OS interim analysis is 24. The second interim analysis of OS will be performed at the planned PFS final analysis, after 185 PFS events have occurred. If the planned final analysis of PFS is not performed due to an early stop for efficacy, then the second interim analysis of OS will be conducted approximately 1 year after the first interim OS analysis. The estimated number of OS events at the second OS interim analysis is 58. The final analysis of OS will take place after the completion of follow-up for all subjects. The estimated number of OS events at the final OS analysis is 161. The information fractions at the two interim OS analyses and the final OS analysis will be calculated based on 161 planned OS events at the final OS analysis. The cumulative alpha spending at the three analyses will be 0.0001, 0.0249, and 0.0250, respectively. If the OS analyses occur at 24, 58, and 161 OS events, the p-value stopping boundaries for the three analyses will be 0.0001, 0.0249 and 0.0003, respectively. The actual p-value stopping boundaries will be derived from the actual number of OS events that occurred. The statistical

significance of OS will be claimed based on the hierarchical testing procedure as specified in [Section 6.3](#).

## 4 ANALYSIS SETS

### 4.1 Intent-To-Treat (ITT) Analysis Set

The intent-to-treat (ITT) analysis set includes all subjects who are randomized, with treatment group designated according to randomization.

This analysis set will serve as the primary analysis set for all efficacy endpoints and demographics.

### 4.2 All-Treated (AT) Analysis Set

The all-treated (AT) analysis set includes all subjects who receive any amount of study drug (duvelisib or ofatumumab), with treatment group designated according to actual study treatment received. The AT analysis set will be the primary analysis set for safety endpoints.

### 4.3 Per-Protocol (PP) Analysis Set

The per-protocol (PP) analysis set includes all subjects in the ITT analysis set who do not violate the terms of the protocol in a way that would significantly affect the study outcome, with treatment group designated according to randomization. Subjects who meet any of the following criteria may be excluded from this analysis set:

- Do not have documented diagnosis of CLL or SLL
- Do not have measurable nodal disease at baseline as determined by the IRC
- ECOG performance status >2
- History of Richter's transformation or prolymphocytic leukemia
- Refractory to ofatumumab (defined as progression or relapse <12 months of receiving ofatumumab monotherapy or <24 months of receiving an ofatumumab-containing regimen)
- Prior exposure to a PI3K inhibitor
- Receive concomitant prohibited anticancer therapy
- Permanent discontinuation from study drug due to non-compliance

The PP analysis set will be a secondary analysis set for selected efficacy analyses.

## 5 STUDY ENDPOINTS

### 5.1 Primary Endpoint

The primary efficacy endpoint PFS is defined as time from randomization to the first documentation of progressive disease (PD) as determined by independent review or death due to any cause.

The censoring method of the primary endpoint can be found in [Appendix A](#). The detailed algorithm will be specified in the Analysis Data Model (ADaM) specifications.

### 5.2 Secondary Endpoints

The secondary efficacy endpoints of the study are:

- Overall Response Rate (ORR), with overall response (based on independent review) defined as best response of complete response/remission (CR), CR with incomplete marrow recovery (CRi), partial response/remission (PR), or PR with lymphocytosis (PRwL), according to the IWCLL or revised IWG Response Criteria, with modification for treatment-related lymphocytosis
- Overall Survival (OS), defined as time from randomization to death
- Lymph node response rate, with lymph node response defined as  $\geq 50\%$  decrease in the SPD of target lymph nodes
- Hematologic improvement rate, defined as any of following hematologic improvement sustained for at least 60 days without transfusion or exogenous growth factors:
  - Neutrophil count  $> 1,500/\mu\text{L}$  or an increase  $\geq 50\%$  from Baseline; or
  - Hemoglobin  $> 11 \text{ g/dL}$  or an increase  $\geq 50\%$  from Baseline; or
  - Platelet count  $> 100,000/\mu\text{L}$  or an increase  $\geq 50\%$  from Baseline
- Duration of Response (DOR), defined as time from the first documentation of response to first documentation of PD or death due to any cause.

Other secondary endpoints of the study are:

- TEAEs and changes in safety laboratory values
- PK parameters derived from plasma duvelisib concentrations and, if applicable, its metabolite(s)

### 5.3 Exploratory Endpoints

The exploratory efficacy endpoints of the study are:

- Improvement in disease-related symptoms of fatigue, weight loss, unexplained fevers and night sweats from Baseline
- Minimal Residual Disease (MRD) in subjects with documented CR or CRi
- Time to Response (TTR), defined as the time from randomization to the first documentation of response (CR, CRi, PR or PRwL)

The QoL endpoints of the study are:

- Health-related QoL of subjects as assessed by the following subject-reported questionnaires:
  - EuroQol-5D (EQ-5D)
  - Functional Assessment of Chronic Illness Therapy-Fatigue (FACIT-F)

The biomarkers of the study are:

- Serum and tissue biomarkers and blood immunophenotype
- Tumor genomic features (eg, DNA sequence variation, DNA copy number variation, and/or RNA expression)
- Germline DNA sequence variations

## 6 GENERAL STATISTICAL METHODS AND DATA HANDLING

### 6.1 General Methods

Summary statistics will be presented by treatment group, unless stated otherwise.

Unless otherwise specified, descriptive statistics for continuous data will include the number of subjects with data to be summarized (n), mean, standard deviation, 25% quartile, median, 75% quartile, and minimum and maximum. The same number of decimal places as in the raw data will be presented when reporting the minimum and maximum, one more decimal place than the raw data will be presented when reporting mean and median, and 2 more decimal places than the raw data will be presented when reporting standard deviation.

Descriptive statistics for categorical/qualitative data will include frequency counts and percentages. The total number of subjects in the treatment group will be used as the denominator for percent calculations, unless stated otherwise. All percentages will be presented with one decimal, unless otherwise specified. Percentages equal to 100 will be presented as 100, and percentages will not be presented for zero frequencies.

Descriptive statistics associated with time-to-event analyses will include the number of events, the number of subjects censored, 25% quartile, median, 75% quartile, and 95% confidence interval for median. These statistics will be presented for all time-to-event analyses, unless stated otherwise.

Listings will be provided for selected endpoints.

### 6.2 Handling of Missing Data

In general, values for missing data will not be imputed unless methods for handling missing data are specified.

#### 6.2.1 Handling of Missing Dates/Months/Years for Adverse Events

Adverse events (AEs) with incomplete onset dates will be handled as follows for the sole purpose of determining treatment emergence (TEAE is defined in [Section 7.3.1](#)):

- If the start/end date of an AE is partially missing, the date will be compared as far as possible with the date of the start of administration of study drug and the date of last dose of study drug plus 30 days. The AE will be assumed to be treatment emergent if it cannot be definitively shown that the AE did not occur or worsen during the treatment-emergent period (worst case approach). The detailed algorithm will be specified in ADaM specifications.
- If the start date is completely missing, an AE will be considered treatment-emergent unless the stop date is before study drug administration.
- If the dose start date is missing for a subject at a data-cut, all AEs of the subject will be considered treatment-emergent.

The original partial or missing date will be shown in listings of AEs.

## 6.2.2 Handling of Missing Dates/Months/Years for Concomitant Medications

Prior or concomitant medications with incomplete start dates will be handled as follows for the sole purpose of determining whether a non-study medication is a concomitant medication:

- If the start/stop date of a medication is partially missing, the date will be compared as far as possible with the date of the start of administration of study drug and the date of last dose of study drug plus 30 days. The medication will be assumed to be concomitant if it cannot be definitively shown that the stop date is before the start of administration of study drug, or the start date is more than 30 days after the last date of administration of study drug. The detailed algorithm will be specified in ADaM specifications.
- If the start/stop dates are completely missing, a medication will be considered concomitant.
- If the dose start date is missing for a subject at a data-cut, all non-study medications of the subject will be considered concomitant.

The original partial or missing date will be shown in listings of all non-study medications.

## 6.2.3 Handling of Missing Dates/Months/Years for Disease History and Prior Therapies

For the purpose of calculating the duration from initial diagnosis, most recent relapse/refractory diagnosis or most recent prior therapy to randomization, partial/missing dates for diagnosis and last prior therapy completion will be imputed as follows:

- If both date and month are missing and the year is prior to the year of screening, the imputed date and month will be 01 July.
- If both date and month are missing and the year is the same as the year of screening, the imputed date will be the middle point between 01 Jan of the year and the screening date. If the middle point falls between two dates, the first of the two dates will be used.
- If date is missing and the month and year are prior to the month and year of screening, the imputed date will be 15th day of the month.
- If date is missing and the month and year are the same as the month and year of screening, the imputed date will be the middle point between the first date of the month and the screening date. If the middle point falls between two dates, the first of the two dates will be used.
- No imputation will be performed if the year is missing.

## 6.3 Multiple Comparisons/Multiplicity Adjustment

Of the secondary endpoints, ORR and OS are designated as key secondary efficacy endpoints. The primary endpoint and key secondary endpoints will be tested at an overall one-sided alpha level of 0.025 based on a gatekeeping approach.

If the primary endpoint is significant, the two key secondary endpoints will be sequentially tested in the order listed above. ORR will be tested at the one-sided 0.025 level only if PFS is declared statistically significant. OS will be tested according to the planned alpha spending specified in [Section 3.5.2](#) only if PFS and ORR are declared statistically significant. If any null hypothesis is not rejected in this sequence of tests, formal sequential testing will be stopped.

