9.4.2 Analysis of Key Secondary Efficacy Endpoints

Of the secondary endpoints, ORR, Lymph Node Response Rate, OS, and Hematologic Improvement Rate are designated as key secondary efficacy endpoints. If the primary endpoint is significant, the four key secondary endpoints will be sequentially tested at the 1-sided 0.025 significance level in the order listed above. If a null hypothesis is not rejected, formal sequential testing will be stopped. The detailed testing strategy will be specified in the SAP.

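### ORR is tested at the full one-sided 0.025 at whichever look PFS succeeds, so the claimed overall 0.025 is not guaranteed for ORR; the likely excess is about 0.001

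*SAP*

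**What the plan says.** SAP V4.0 Section 6.3 makes the family-wide claim: "The primary endpoint and key secondary endpoints will be tested at an overall one-sided alpha level of 0.025 based on a gatekeeping approach". For ORR it adds: "ORR will be tested at the one-sided 0.025 level only if PFS is declared statistically significant". OS comes third and may be tested only after both PFS and ORR have succeeded.

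On timing, Section 3.5.1 says: "There will be two planned analyses for PFS, one interim analysis and one final analysis". The efficacy levels are 0.0015 at 93 events and 0.0245 at 185. Section 3.5.2 gives OS three looks with their own spending, and: "The first interim analysis of OS will be performed at the time of the planned PFS interim analysis after 93 PFS events have occurred". Section 3.5 introduces all of this with: "Interim and final analyses are planned for PFS and OS". ORR is not named there, and no section gives it a spending function, a boundary or a data cut.

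Protocol 9.4.2 uses the same level for a longer list ("the four key secondary endpoints will be sequentially tested at the 1-sided 0.025 significance level") and leaves the detailed strategy to the SAP. SAP V4.0 reduces the list to ORR and OS.

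**The concern.** ORR is formally tested once, which looks safe. The difficulty is how the look is chosen. OS has a look at the PFS interim but cannot be tested until ORR has succeeded, so a formal OS test there needs an ORR test there. If PFS does not cross at the interim, ORR waits for the final analysis. The PFS result therefore selects the ORR look.

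That selection is not neutral. Progression and response come from the same central review of the same assessments (Protocol 6.3.9.3; SAP 7.2), so a favourable chance result in one tends to accompany a favourable result in the other. ORR can also change between looks, because SAP 7.2.2.1 defines it from the best response over the whole study. Giving a correlated secondary endpoint full alpha at whichever look the primary crosses does not in general hold its error at that alpha. At stake is a confirmatory claim on ORR, and ORR is the only step between PFS and OS. PFS itself is unaffected.

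**Working it through.** **1. Reproduce the PFS design.** The Lan-DeMets O'Brien-Fleming spend at fraction t is 2[1 − Φ(2.2414/√t)]. At t = 0.5 this is 0.00153, so c1 = 2.963 and the critical HR is exp(−2 × 2.963/√92.5) = 0.540. Solving for the final look gives c2 = 1.969, p = 0.0245 and HR = exp(−2 × 1.969/√185) = 0.749 (plan: 0.748). Power at HR 0.6 is 93.4% (plan: about 93%). The interim drift is 0.5108 × √(92.5/4) = 2.456, so PFS crosses at the interim with probability 1 − Φ(2.963 − 2.456) = 0.31. The stated design reproduces.

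**2. ORR error under the plan.** Let P1, P2 be the PFS statistics and S1, S2 the ORR statistics at the two looks, with no true ORR effect:

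error = Pr(P1 > c1, S1 > 1.96) + Pr(P1 ≤ c1, P2 > c2, S2 > 1.96)

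The correlations are corr(P1,P2) = √(93/185), corr(S1,S2) = √q, PFS with ORR at the same look = ρ, and corr(P1,S2) = ρ√q. Here q is the share of final ORR information available at the interim. Neither ρ nor q is in the documents, so both are assumptions. Results at HR 0.6 by numerical integration (simulation agrees to within 0.0002):

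| q | ρ = 0.3 | ρ = 0.5 | ρ = 0.7 |
|---|---|---|---|
| 0.50 | 0.0268 | 0.0284 | 0.0291 |
| 0.70 | 0.0259 | 0.0269 | 0.0271 |
| 0.80 | 0.0255 | 0.0262 | 0.0263 |
| 0.85 | 0.0253 | 0.0259 | 0.0259 |

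**3. Where there is no excess.**
- ρ = 0: the error is 0.025 × 0.934 = 0.0234.
- q = 1: S1 = S2, so the error is at most Pr(S > 1.96) = 0.025.
- PFS null: the error is at most the chance of rejecting PFS, which is 0.025.

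**4. Which q is plausible.** A linear 11-month ramp to 30 per month followed by 5 months at peak gives 30 × (5.5 + 5) = 315. Scaling to 300 at 16 months makes the peak 30 × 300/315 = 28.57 per month. Cycle 3, 5 and 7 Day 1 fall 49, 105 and 161 days after first dose (Protocol 4.1), that is 1.610, 3.450 and 5.290 months. At month 17, with dosing on the day of randomization, the numbers not yet there are:
- Cycle 3: (16 − 15.390) × 28.57 = 17.4
- Cycle 5: (16 − 13.550) × 28.57 = 70.0
- Cycle 7: (16 − 11.710) × 28.57 = 122.6

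Dosing at the 7-day limit adds 0.230 × 28.57 = 6.6 to each. So about 17 to 24 of 300 have not reached Cycle 3 Day 1, and about 70 to 77 have not reached Cycle 5 Day 1. All of them count in the ORR denominator.

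The only response timing in the documents is Protocol 1.5: of 12 partial responses at 25 mg BID or less, 6 came after 2 cycles, 4 after 4 and 2 after 6. Weighting the shares reached (0.942, 0.767, 0.591) gives (6 × 0.942 + 4 × 0.767 + 2 × 0.591)/12 = 0.83. With the 7-day delay it is (6 × 0.920 + 4 × 0.745 + 2 × 0.570)/12 = 0.80. So q is probably about 0.80 to 0.85.

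**5. Other effect sizes.** HR 0.6 is not the least favourable case. At HR 0.7 and ρ = 0.7 the error is 0.0309 at q = 0.50 and 0.0270 at q = 0.82.

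**The case against.** The strongest reply is that the excess is tiny and conditional. It needs a real PFS effect, no ORR effect, positive correlation and ORR data that move between looks, all together. The largest figures assume that only half of the ORR information is in at the interim, whereas the phase 1 timing points to about 80%. This stands, and it governs the size given below. That timing is itself a proxy: 12 responders, duvelisib only.

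A second reply is that the SAP never says ORR is tested at the interim. That also stands: the look is inferred. It is the natural reading, because no other time is given and the first OS look cannot be formal without it, but the SAP should say so.

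Three stronger readings are tempting and are not supported:
- That control for ORR simply fails. It does not in the three cases in step 3 of the working.
- That the error reaches 0.0415. That is the upper bound at q = 0.50; coming close to it (0.0412) takes a correlation of 1 and an HR near 0.81.
- That immature responses at month 17 inflate the error by themselves. They affect power and estimation. The error rises only through selection of the look by a correlated PFS result.

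**Conclusion.** The concern holds as a gap between the claim and the procedure. SAP 6.3 promises overall one-sided 0.025, and the rule for ORR does not guarantee it. At the design HR of 0.6 and assumed correlations of 0.3 to 0.7, the likely ORR error is about 0.025 to 0.026, an excess of about 0.001. It rises to about 0.029 if only half of the ORR information is in. These sizes rest on the assumed correlation, the assumed information share, the scaled accrual ramp and the inferred timing of the ORR test. If the ramp is left unscaled (300 reached at 15.5 months), the counts in step 4 fall to about 3-10 and 59-65, and the information share is somewhat higher. Because the excess is small, the reason to act is that the SAP claims strict control and the repair is cheap.

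**What to change.** In SAP 6.3, state at which analysis and on which data cut ORR is tested. Then choose one of two rules:

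- **A two-look boundary for ORR**, for example 0.0015 if tested at the interim and 0.0245 at the final. The worst-case error, Pr(S1 or S2 crosses), is 0.0250 at q = 0.50 and 0.0245 at q = 0.80, whatever the correlation or PFS effect. It is 0.0252 at q = 0.40 and 0.0254 at q = 0.30, so this pair holds 0.025 only when at least half of the ORR information is in at the interim.
- **One ORR test at 0.025 on a data set fixed in advance**, the same whichever look PFS crosses. No assumption about q is needed.

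The cost is a few sentences in the SAP. Protocol 9.4.2 defers the detailed strategy to the SAP, so an SAP change may suffice, though its ORR level should be aligned when it is next amended. The price of the first rule is a stricter ORR threshold if PFS stops early. The price of the second is a later ORR test, with formal OS testing waiting for it.
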